## **5.8. Adverse Events and Missing Data**

A treatment-emergent adverse event (TEAE) is any AE either reported for the first time or worsening of a pre-existing event after first dose of study medication. Analysis of AEs will be limited to TEAEs, but data listings will include all AEs.

Severity of AEs will be described and graded using the National Cancer Institute (NCI) Common Terminology Criteria for Adverse Events (CTCAE). CTCAE v4.03 is used for this protocol. If the toxicity is not included in the CTCAE v4.03 criteria it will be rated on a 1 to 4 scale as follows: mild = 1; moderate = 2; severe = 3; and life-threatening = 4.

An AE will also be assessed by its relationship to study medication as well as by seriousness. These assessments will be directly from data collected on eCRFs and are described in details in the protocol.

Any missing onset date, causality, or severity must be queried for resolution. Unsolved missing values will be handled according to the following rules:

- An unsolved missing causality will be considered treatment related
- An unsolved missing severity will be identified as an unknown severity

- For purposes of analysis, all AEs will be considered TEAEs unless the AE can unequivocally be defined as not treatment emergent. Therefore, an unsolved missing onset date will be considered treatment emergent, with the following examples illustrating exceptions:
  - If the stop/resolution date is before the first dose date on Day 1, then the AE will be considered as not being treatment emergent.
  - If both the month and day are missing, and the last day of the year is before the first dose date on Day 1, then the AE will not be considered treatment emergent.
  - If only the day is missing, and the last day of the month is before the first dose date on Day 1, then the AE will not be considered treatment emergent.
  - If only the day is missing, and the first day of the month is after the first dosing date on Day 1, then the AE will be considered treatment emergent.

## **5.9. Variable Definitions and/or Derivation Rules**

### **5.9.1. Spleen Volume Value at Week 24**

If Week 24 spleen volume value is obtained in the manner of by-schedule visit, it will be used as the analytic value for study analysis regardless of the actual time window it falls into. However, if the only values available are from unscheduled visits, then the last available value within the window of Day 141 to Day 175 (=168 + 7 days) will be used as Week 24 spleen volume analytic value. When spleen volume data are available for both by-schedule and unscheduled visits (within the window), the value from the scheduled visit will be used.

### **5.9.2. Total Symptom Score**

#### **5.9.2.1. Daily Total Symptom Score**

Daily total symptom score is derived as the sum of 6 individual symptom scores (the total score excludes scores for degree of inactivity); this score will be missing if there are any missing individual scores. Observations with an un-resolved missing date will be excluded from analysis.

#### **5.9.2.2. Baseline Total Symptom Score**

Baseline value of total symptom score is derived as the average of the prorated daily total symptom score for the 7 days before the first dose on Day 1 (ie, from Day -7 to Day -1). If  $\geq 4$  daily total symptom score values are missing during this period of time, the baseline total symptom score value is set as missing.

### 5.9.2.3. Total Symptom Score at Weeks 4, 8, 12, 16, 20, and 24

Week X (where X = 4, 8, 12, 16, 20, and 24) total symptom score is derived as the average of the daily total symptom scores collected from the last 28 consecutive days covering the interval between up to Day  $(X+n)*7$ , where n is 1 for Week 24 and 0 otherwise, and Day  $(X-4)*7 + 1$  as presented in Table 4.

**Table 4: Windows for Total Symptom Score at Given Study Time Points**

Study Time Point	Window	Note
Week 4	Day 1 to Day 28	
Week 8	Day 29 to Day 56	
Week 12	Day 57 to Day 84	
Week 16	Day 85 to Day 112	
Week 20	Day 113 to Day 140	
Week 24	Last 28 days of the window from Day 141 to the last day when daily total symptom score value is available and it is $\leq$ Day 175.	If the last evaluation day is before Day $168-7 = 161$ then total symptom score will be set as missing for Week 24.

Total symptom score for given study time points displayed above will be missing if there are more than 8 values missing in the 28-day window. It should be noted that a score of 0 is not a missing value.

### 5.9.3. Dosing Level and Compliance

#### 5.9.3.1. Final Titrated Dose Level

The analytic value of the last titrated dose level will be derived as the average of the total daily dose (excluding periods of dose interruption) during the time interval of Day 141 and Day 168, or the last 28 days of available dosing data (for subjects who discontinued treatment early). All available data points in the time interval will be used for this calculation.

#### 5.9.3.2. Last Average Daily Dose Level During the Treatment Period

For subjects who have the analytic value of the last titrated dose level derived, the last average daily dose level during the treatment period will be the same. For subjects who discontinued and do not have last titrated dose level derived, it will be the average of the last 28 days (excluding periods of dose interruption) of treatment. For subjects who discontinued study before Day 28, it is the same as the average daily dose level during the study.

### **5.9.3.3. Study Drug Compliance**

Study drug compliance (%) is calculated as

$$100 \times [\text{total dose taken}]/[\text{total dose prescribed}]$$

where total dose taken is calculated as before, and total dose prescribed will be based on the dosing prescription as collected through the CRF pages of EX domain. If prescribed dose collected from EX domain is 0, it also indicates a prescribed dose interruption; in addition, dose reduction or increase as recorded in EX domain are all regarded as investigator-mandated prescriptions on study drug for the subjects to follow.

Study drug compliance will be calculated only for the pre-extension phase of 24 weeks. Based on need of exploratory analysis, compliance for other periods may be derived as well.

Because of the eCRF design, other than calculating study drug compliance, data collected on the EX domain of the eCRF will be used as actual study drug administration information in order to carry out other dose-response type analyses, such as AEs by the dose level before the AE (Section 5.9.3.4). In the case of a serious discrepancy between the prescribed dose and the dose received, additional actions may be taken to modify data entries.

### **5.9.3.4. Last Dose Level Prior to an Adverse Event**

The last dose level prior to an AE is derived as the last non-zero dose (from EX domain) prior to the day an AE occurred. The reason to use “prior to the day” which excludes the day on which an AE occurred is that daily dose is divided into morning and evening doses and no dose administration time is collected on eCRF, making the last dose prior to an AE difficult to verify if “on the same day” dose levels are also included in the derivation.

It is noted that the data collected through the EX domain is treated as actual doses (rather than the prescribed dose schedule, as is the case of deriving compliance, defined earlier). This approach is used throughout when dose-response analyses (for both safety and efficacy) are carried out.

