## 5.2. Treatment Groups

Subjects will be summarized as 1 group regardless of dose titration. For certain summaries of AEs by dose received (details can be found in the appendix of table shells), subjects will be grouped into the following categories:  $\leq 5$  mg,  $> 5$  to 10 mg,  $> 10$  to 15 mg,  $> 15$  to 20 mg,  $> 20$  to 25 mg, and  $> 25$  mg based on the final titrated total daily dose (see [Section 5.9.3.1](#)).

In addition, for the summary of exposure, final titrated dose groups as defined above may be used as treatment groups and additional efficacy analysis may utilize these dose categories.

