14.3.2.8	Summary of Subjects Reporting Treatment-Emergent Adverse Events (All Causalities) Leading to On-Study Death by MedDRA System Organ Class, Preferred Term, and Dose Level Ever Received	Safety
Safety: Laboratory Data		
14.3.3.1.1	Summary of Laboratory Values – Hematology	Safety
14.3.3.1.2	Shift Summary of Laboratory Values in Normal Ranges - Hematology	Safety
14.3.3.2.1	Summary of Laboratory Values – Serum Chemistry	Safety
14.3.3.2.2	Shift Summary of Laboratory Values in Normal Ranges – Serum Chemistry	Safety
14.3.3.3.1	Summary of Laboratory Values – Coagulation	Safety
14.3.3.3.2	Shift Summary of Laboratory Values in Normal Ranges – Coagulation	Safety
14.3.3.4.1	Summary of Laboratory Values – Urinalysis	Safety
14.3.3.4.2	Shift Summary of Laboratory Values in Normal Ranges – Urinalysis	Safety
14.3.3.5.1	Shift Summary of Laboratory Values in CTC Grade - To the Worst Abnormal Value (Tests with One Directional CTC Grade)	Safety

Table Number	Title	Population
14.3.3.5.2	Shift Summary of Laboratory Values in CTC Grade - To the Worst Abnormal Value (Tests with Two Directional CTC Grade)	Safety
14.3.3.6.1	Summary of Subjects with Treatment Emergent Thrombocytopenia of Grade 4 as Derived From Laboratory Data by Dose Level Ever Received	Safety
14.3.3.6.2	Summary of Subjects with Treatment Emergent Anemia of Grade 4 as Derived From Laboratory Data by Dose Level Ever Received	Safety
Safety: Vital Signs		
14.3.4.1	Summary of Systolic Blood Pressure	Safety
14.3.4.2	Summary of Diastolic Blood Pressure	Safety
14.3.4.3	Summary of Heart Rate	Safety
14.3.4.4	Summary of Respiratory Rate	Safety
14.3.4.5	Summary of Body Temperature	Safety

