14.3.3.1.2	Shift Summary of Laboratory Values in Normal Ranges - Hematology	Safety
14.3.3.2.1	Summary of Laboratory Values – Serum Chemistry	Safety
14.3.3.2.2	Shift Summary of Laboratory Values in Normal Ranges – Serum Chemistry	Safety
14.3.3.3.1	Summary of Laboratory Values – Coagulation	Safety
14.3.3.3.2	Shift Summary of Laboratory Values in Normal Ranges – Coagulation	Safety
14.3.3.4.1	Summary of Laboratory Values – Urinalysis	Safety
14.3.3.4.2	Shift Summary of Laboratory Values in Normal Ranges – Urinalysis	Safety
14.3.3.5.1	Shift Summary of Laboratory Values in CTC Grade - To the Worst Abnormal Value (Tests with One Directional CTC Grade)	Safety
14.3.3.5.2	Shift Summary of Laboratory Values in CTC Grade - To the Worst Abnormal Value (Tests with Two Directional CTC Grade)	Safety

PROTOCOL: INCB 18424-258  
 DRUG/INDICATION: Ruxolitinib/Myelofibrosis

(Page 1 of 1)  
 VERSION: Final

Table 14.3.3.6.1

Summary of Subjects with Treatment Emergent Thrombocytopenia of Grade 4 as Derived from Laboratory Data  
 by Last Dose Before Onset  
 (Population: Safety Evaluable Subjects)

MedDRA Preferred Term	All Subjects (N=xx)	Dose Level (mg) Subjects Ever Received					
		<=5	>5 10	>10 15	>15 20	>20 25	>25
		N=xx	N=xx	N=xx	N=xx	N=xx	N=xx
Number (%) of Subjects With Grade 4 Thrombocytopenia [1]	xx ( xx.x)	xx xx%	xx xx%	xx xx%	xx xx%	xx xx%	xx xx%

PROGRAM\OUTPUT: T\_xxxx.SAS\T\_xxxxx.LST

DATE (TIME) : DDMMYY (HH:MM)

Treatment-Emergent AEs: AEs that began or worsened from baseline following the first administration of study drug.

Note: Subjects are counted only once under in the lowest dose group.

Note: N=the number of subjects who ever took a dose within the dose group, based on which the percent is calculated.

Note: AEs that occurred following the date of treatment crossover were not included.

[1] Grade 4 Thrombocytopenia is defined as any occurrence of a treatment emergent hematology lab below 25 GI/L

Reference: Listing 16.2.8.1.4

PROTOCOL: INCB 18424-258  
DRUG/INDICATION: Ruxolitinib/Myelofibrosis

(Page 1 of 1)  
VERSION: Final

Table 14.3.3.6.2

Summary of Subjects with Treatment Emergent Anemia of Grade 4 as Derived from Laboratory Data  
by Last Dose Before Onset  
(Population: Safety Evaluable Subjects)

NOTE TO THE PROGRAMMER: similarly program this as Table 14.3.3.6.1, just need to update footnote about G4 anemia.

NOTE: the following vital sign tables will be programmed according to standard output.

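### SAP 5.2 groups AE-by-dose summaries by final titrated dose, against SAP 5.9.3.4 and the shells, and the note in shell 14.3.3.6.1 adds a conflicting lowest-dose rule

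*SAP*

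**What the plan says.** - SAP 5.9.3.4 assigns an AE to a dose that "is derived as the last non-zero dose (from EX domain) prior to the day an AE occurred". SAP 5.9.3.3 names AEs by the dose before the event as an example of the dose-response analyses and points to 5.9.3.4.
- SAP 5.2 says: "For certain summaries of AEs by dose received (details can be found in the appendix of table shells), subjects will be grouped" into six daily-dose bands "based on the final titrated total daily dose". SAP 5.9.3.1 derives that dose as the "average of the total daily dose (excluding periods of dose interruption) during the time interval of Day 141 and Day 168", or over the last 28 days of dosing data for early discontinuers.
- SAP 10.1 lists Table 14.3.3.6.1 as "Summary of Subjects with Treatment Emergent Thrombocytopenia of Grade 4 as Derived From Laboratory Data by Dose Level Ever Received".
- In SAP Appendix B the shell of the same table is titled "by Last Dose Before Onset". Its column head still refers to dose levels ever received, and each column N is the number of subjects who ever took a dose in that band. A Grade 4 event "is defined as any occurrence of a treatment emergent hematology lab below 25 GI/L". A note adds: "Subjects are counted only once under in the lowest dose group".
- Shells 14.3.2.1 and 14.3.2.2.2 count a repeated AE at the lowest dose at which its worst grade was seen.

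**The concern.** Dose in this trial responds to the event being tabulated. Protocol 8.6.2 requires a hold when platelets fall below 25 x 10^9/L. Protocol 8.6.3.1 then allows a restart only at 5 mg once daily, with limited re-escalation. A subject's dose in the last four weeks of the core phase is therefore partly a consequence of an earlier Grade 4 count. Grouping by it moves events from the dose that preceded them to the dose that followed.

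The lowest-dose note has a related weakness. It suits a design in which dose only rises. Here dose drops to 5 mg/day after each platelet hold, so a recurrence soon after a restart can pull the subject into the lowest column, away from the dose at first onset.

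Table 14.3.3.6.1 is the by-dose display of a named safety endpoint (SAP 3.1.2.2). It also bears on the secondary objective of finding a dosing strategy for patients with low platelets. At stake is whether low doses appear more toxic than they are.

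**Working it through.** **1. Figures in the documents.** Interim Grade 4 platelet rate (protocol 4.1.5): 8/50 = 16%, so 0.16 x 150 = 24 expected subjects. No document gives a Grade 4 rate by dose, so there is no stated gradient to reproduce.

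**2. What the shells do.** The figures in shell 14.3.2.1 are draft values, shown for layout only.
- Column Ns: 2 + 23 + 14 + 7 + 1 = 47, for 23 subjects. Final-dose groups would sum to 23, so the shell does not use the 5.2 grouping.
- Subjects with a TEAE: 1 + 3 + 5 + 1 + 0 = 10, equal to the total of 10. TEAEs reported: 1 + 8 + 21 + 3 + 0 = 33, equal to the total.
- Percentages are numerator over ever-received N: 1/2 = 50.0, 3/23 = 13.0, 5/14 = 35.7, 1/7 = 14.3. All match.

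The numerator counts each subject once and the denominator overlaps across columns. That is a coherent design, and it is not the 5.2 grouping.

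**3. One subject who follows the protocol.** 20 mg/day from Week 8; count below 25 at Week 10; restart at 5 mg/day at Week 12; second count below 25 at Week 13; restart at 5 mg/day at Week 15; 10 mg/day from Week 17. The column is >15 to 20 by dose before first onset, <=5 by the lowest-dose note applied to the two events, and >5 to 10 by final titrated dose.

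**4. When final-dose grouping reverses the order.** Take 8 Grade 4 and 42 event-free subjects. Let s and q be the shares of each that end at 10 mg/day or below.
- Low-dose rate = 8s/(8s + 42q); high-dose rate = 8(1 - s)/[8(1 - s) + 42(1 - q)]. The low-dose rate is the larger exactly when s > q.
- q = 0.3, s = 0.75: 6/18.6 = 32% against 2/31.4 = 6%. Reversed.
- q = 0.3, s = 0.25: 2/14.6 = 14% against 6/35.4 = 17%. Not reversed.

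**5. Simulation of the titration, hold and restart rules over 24 weeks, near 16% incidence.** The true hazard rises with dose. Hazard ratio, escalation, re-escalation and discontinuation rates are assumptions.

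Model A: hazard ratio 1.25 or 2 per 5 mg/day, gamma frailty variance 1 or 3, dose reductions for counts of 25 to 35 at 0 to 2 times the Grade 4 hazard, ceiling 20 mg/day.
- No dropout, dose before first onset: 2.6% to 6.4% in the >5 to 10 column against 6.9% to 17.7% in >15 to 20; higher dose worse in 72 of 72 scenarios.
- No dropout, final titrated dose: 17.8% to 37.5% at 10 mg/day or below against 1.1% to 12.7% in >15 to 20; lower dose worse in 72 of 72.
- Dropout at first event added, at 0%, 12.5% or 50% of Grade 4 subjects: reversed in 72 of 72. At 100%: 16 of 24. Across these 96 scenarios the 5.9.3.4 order held in 88.

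Model B: hazard ratio up to 3, doses above 20 mg/day allowed, no reductions for counts of 25 to 35 (which would soften a reversal).
- Hazard ratio 2, escalation probability 0.5 per visit, 12.5% discontinuing, half re-escalating. Final dose gives 73% at 10 mg/day or below against 7% above. Dose before onset over ever-received N gives 2%, 4%, 11%, 7% and 17% in the five columns above 5 mg, broadly rising.
- All Grade 4 subjects discontinuing: hazard ratio 3 gives 12% against 16% (escalation 0.2) and 15% against 17% (0.35), not reversed; hazard ratio 2 with escalation 0.2 gives 16% against 14%.
- Half discontinuing, hazard ratio 3, escalation 0.2: 22% against 15% when cut at 10 mg/day, but 17% against 19% when cut at 15.

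**6. Size of the lowest-dose note.** In Model A without dropout it moved 0.8% to 12.4% of Grade 4 subjects below their first-onset column: 0.008 x 24 = 0.2 to 0.124 x 24 = 3.0 subjects. Read literally as the lowest dose taken, it would put every Grade 4 subject at 10 mg/day or below, because all start at 5 mg twice daily.

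**The case against.** The case on the other side is substantial.

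- A reader might infer that the SAP holds four mutually incompatible dose definitions. It does not. Last dose before onset can place the event, dose ever received can set the column N, and lowest dose at worst grade can break ties for repeated AEs. The draft numerators in step 2 behave this way.
- A reader might also infer that nothing indicates the intended basis. SAP 5.9.3.3 and 5.9.3.4 do, and the shell title of 14.3.3.6.1 agrees. SAP 5.2 covers only certain summaries and refers to the shells for details. No AE shell uses final titrated dose.
- A reversal is not certain. An early discontinuer's last 28 days of dosing can be the pre-event dose, which preserves the order.
- The displays are descriptive. Listing 16.2.8.1.4 gives haematology data for Grade 4 subjects, and SAP 9.5 plans a longitudinal platelet analysis against exposure, so dosing strategy does not rest on this table alone.

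All of this stands, and it narrows the point without removing it. The reference in 5.2 is for details, while the same sentence fixes the grouping, and that grouping is wrong for AEs. In shell 14.3.3.6.1 the lowest-dose note carries no worst-grade condition, so it is not the tie-break of the other shells and conflicts with the shell's own title.

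**Conclusion.** Two stated rules would misplace Grade 4 events by dose if followed: the final-dose grouping in SAP 5.2, and the lowest-dose note in shell 14.3.3.6.1. That table also carries different titles in the list and the shell.

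Under 5.2 the gradient would be distorted and, with few Grade 4 subjects discontinuing, probably reversed. The interim reports one withdrawal for thrombocytopenia against eight Grade 4 subjects: 1/8 = 12.5% if that subject was one of the eight. Eight of the 50 subjects discontinued before Week 24 for any reason, and the documents do not say how many of those had a Grade 4 count, so the true share could be higher. The documents do not support saying that the planned table will show a reversed gradient: the shells do not specify such a table, and the direction depends on assumed rates of restart, re-escalation and discontinuation.

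The lowest-dose note matters less, at about 0 to 3 of 24 subjects under Model A, unless it is taken as the lowest dose ever received. The overall Grade 4 proportion and the co-primary correlations are unaffected. The correction should be made before the tables are programmed.

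**What to change.** - In SAP 5.2, remove final titrated dose as the AE grouping, keep it for efficacy and exposure, and refer to 5.9.3.4 for AEs.
- State once that the numerator is placed by the last non-zero dose before first onset and that the denominator is the subjects who ever took that dose level.
- In shells 14.3.3.6.1 and 14.3.3.6.2, replace the lowest-dose note with dose before first onset. Make the SAP 10.1 titles, shell titles and column heads agree.

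The cost is SAP and shell wording plus programming; dosing records, AE onset dates and laboratory dates are already collected. The drawback is that recurrences after a restart would appear only in a listing. The table also remains a description of titrated, non-randomised dose. Changing the worst-grade tie-break in the other AE shells, adding person-time by dose level, and deleting the leftover crossover note in shell 14.3.3.6.1 are optional and not part of the error.

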## **5.9.4. Blood Transfusion Independence at Baseline**

Transfusion independence at baseline is defined in 2 ways.

1. It is defined as receiving no transfusions (of red blood cell products) in the 8 weeks before Day 1.
2. It is defined as receiving no transfusions (of red blood cell products) in the 12 weeks before Day 1.

### **5.9.5. Blood Transfusion Independence at Post-Baseline**

Transfusion independence during post-baseline period is defined in 2 ways.

1. It is defined as receiving no transfusions (of red blood cell products) during the final 8 weeks of a subject's participation before the data cutoff date.
2. It is defined as receiving no transfusions (of red blood cell products) during the final 12 weeks of a subject's participation before the data cutoff date.

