4.1.5. Interim Analysis Data from Study INCB 18424-258

In Study INCB 18424-258, subjects with platelet counts of 50 to $100 \times 10^9/L$ were enrolled to begin administration of ruxolitinib at 5 mg BID, which is a dose that represents a conservatively low starting dose, that data from earlier studies suggested should have a limited impact on platelet count. Subjects could then titrate their dose to an appropriate dose that offers benefit (eg, symptomatic and/or spleen size improvements) with cautious monitoring to avoid levels of thrombocytopenia associated with higher risk of spontaneous hemorrhage. Ruxolitinib administration was interrupted for a platelet count below $25 \times 10^9/L$ or for Grade 2 or higher hemorrhage events.

The study is currently in the enrollment phase; however, an interim analysis was conducted based on a data cutoff when it was expected that at least 20 subjects would have completed 24 weeks of treatment. At the time of the interim analysis, a total of 50 subjects had enrolled in the study. Of the 50 subjects enrolled, 33 (66.0%) subjects completed the Week 24 visit,

8 (16.0%) discontinued prior to Week 24, and 9 (18.0%) subjects remained on study and had not yet completed their Week 24 visit.

Most subjects were titrated to a ruxolitinib dose of 10 mg BID or higher by Week 24 and 20.0% of subjects had a $\geq 35\%$ reduction in spleen volume at Week 24. This is consistent with the proportion of subjects in Study INCB 18424-351 who had a $\geq 35\%$ reduction in spleen volume at Week 24 who initiated treatment at a dose of 15 mg BID (21.8%), and substantially higher than that observed for placebo-treated subjects in Study INCB 18424-351 (1.7%). In addition, Mesa et al (2011) has shown that a spleen volume reduction of $\geq 10\%$ is associated with meaningful improvements in symptoms and other measures of patient-perceived benefit (Patient Global Impression of Change [PGIC] and Myelofibrosis Symptom Assessment Form [MFSAF v2.0]).

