 VERSION: Final

Table 14.1.6.1

Summary of Change in Status of Blood Component Transfusion Dependency by Baseline Platelet Count Group  
 (Population: Safety Evaluable Subjects)

Pattern of Change in Dependency Status	Time Interval	Baseline Platelet Count Group					
		50-75 GI/L		>75 GI/L		Total	
		N	n (%)	N	n (%)	N	n (%)
Depend. to Indep.	8 Weeks before Day 1 to Final 8 Weeks	xx	xx(xx.x)	xx	xx (xx.x)	xx	xx (xx.x)
	12 Weeks before Day 1 to Final 12 Weeks	xx	xx(xx.x)	xx	xx (xx.x)	xx	xx (xx.x)
Indep. to Depend.	8 Weeks before Day 1 to Final 8 Weeks	xx	xx(xx.x)	xx	xx (xx.x)	xx	xx (xx.x)
	12 Weeks before Day 1 to Final 12 Weeks	xx	xx(xx.x)	xx	xx (xx.x)	xx	xx (xx.x)

PROGRAM\OUTPUT: T\_XXXXX.SAS\T\_XXXX.LST

DATE (TIME) : ddmmyyyy (hh:mm)

Note 1: N = # subjects at the beginning of the first interval, and n (%) = # (%) subjects at the end of the second interval. The first interval covered within 8 (or 12) weeks prior to Day 1, and the second interval covered last 8 (or 12) weeks after Day 1. Percents are calculated as  $n/N \times 100$  for each row of each group.

Note 2: Transfusion dependence is defined as subjects received at least 1 unit of red blood cell product(s) during the given period. Independence is defined as subjects received 0 unit of red blood cell product(s) during the given period.

Reference: xxxx

PROTOCOL: INCB 18424-258  
 DRUG/INDICATION: Ruxolitinib/Myelofibrosis

(Page 1 of 1)  
 VERSION: Final

Table 14.1.6.2

Summary of Blood Component Transfusions by Baseline Platelet Count Group  
 (Population: Safety Evaluable Subjects)

Variable	Baseline Platelet Count Group		Total (N =xx)
	50-75 GI/L (N = xx)	> 75 GI/L (N = xx)	
Monthly Units of RBC Transfusion: Baseline			
n			
Mean (Std)			
Median			
Min, Max			
Total Units of RBC Transfusion: Post-Baseline			
n			
Mean (Std)			
Median			
Min, Max			
Monthly Units of RBC Transfusion: Post-Baseline			
n			
Mean (Std)			
Median			
Min, Max			

PROGRAM\OUTPUT: T\_XXXXX.SAS\T\_XXXX.LST

DATE (TIME): ddmmmyyyy (hh:mm)

Note 1: Total units = all units during the treatment phase from Day 1 to the last scheduled visit.  
 Note 2: Monthly units = total units divided by the treatment duration (in months where 1 month = 30.4375 days).  
 Reference: Listing XXXXX.

PROTOCOL: INCB 18424-258  
 DRUG/INDICATION: Ruxolitinib/Myelofibrosis

(Page 1 of 1)  
 VERSION: Final

Table 14.2.1.1

Summary of Correlation of Final Titrated Dose vs. Percent Change from Baseline in Spleen Volume at Week 24  

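### Post-baseline transfusion status is judged on whatever follow-up exists, so short follow-up can make the dependence shift table look more favourable than full follow-up would.

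*SAP*

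**What the plan says.** SAP 5.9.4 sets the baseline status on a fixed look-back; the longer version is "receiving no transfusions (of red blood cell products) in the 12 weeks before Day 1". SAP 5.9.5 sets the post-baseline status as "receiving no transfusions (of red blood cell products) during the final 8 weeks of a subject's participation before the data cutoff date" or "receiving no transfusions (of red blood cell products) during the final 12 weeks of" that same participation. It gives no minimum duration and no rule for a subject with less time than the window. SAP 6.8, which calls for the shift summary by baseline platelet group, adds none.

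The shell for Table 14.1.6.1 in SAP Appendix B makes the rule operational:

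- Its first note says "the second interval covered last 8 (or 12) weeks after Day 1", so time before Day 1 does not fill a short window.
- Its second note says "Transfusion dependence is defined as subjects received at least 1 unit of red blood cell product(s) during the given period" and "Independence is defined as subjects received 0 unit of red blood cell product(s) during the given period". The length of the period plays no part.
- Percentages are n/N, where N is everyone with the given baseline status.
- There is no row for subjects who left early or could not be evaluated.

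The table runs on the safety population, which needs only one dose (SAP 5.3.1). On early departure, Protocol 4.1.5 reports that of 50 subjects at the interim analysis "8 (16.0%) discontinued prior to Week 24"; a further 9 had not yet reached that visit.

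**The concern.** The two ends of the shift are measured with different rulers. At a given transfusion rate, a shorter window is less likely to contain a transfusion. A subject can therefore move from dependent to independent simply because observation stopped. The same mechanism hides some moves in the other direction. Both distortions favour the drug relative to full follow-up, and both grow with early dropout.

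Elsewhere the SAP deals with incomplete data explicitly. A 28-day total symptom score is set to missing when more than 8 days are missing (SAP 5.9.2.3, Table 4). The spleen-response shell (Table 14.2.2.2) shows discontinuation before Week 24 as a reason for not responding. Transfusion status has no such provision. What is at stake is the reading of one descriptive table, and of the post-baseline dependent proportion in SAP 6.8 that uses the same definition.

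**Working it through.** The documents give no figure for transfusion independence, so there is none to reproduce. The interim dropout figure checks: 8/50 = 16.0%.

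**Step 1: trace the rule.** Take a subject with at least 1 unit in the 12 weeks before Day 1 who leaves at Week 3 with no transfusion on study. The status at baseline is dependent. The period available after Day 1 holds 0 units, so the shell's definition gives independent. The subject is in N for the dependent group and in n for the move to independence. If the same subject had been transfused once in those 3 weeks, the status would stay dependent. Misclassification is therefore possible, not automatic.

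**Step 2: share with a short window.** Assumptions not in the documents: dropout is even over 24 weeks, and dependent subjects leave at the overall 16%.

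| Reading of participation | Under 12 weeks | Under 8 weeks |
|---|---|---|
| Ends at drug stop | 16% × 12/24 = 8% | 16% × 8/24 = 5.3% |
| Includes 30-day follow-up (4.3 weeks) | 16% × 7.7/24 = 5.1% | 16% × 3.7/24 = 2.5% |
| Includes 37-day follow-up (5.3 weeks) | 16% × 6.7/24 = 4.5% | 16% × 2.7/24 = 1.8% |

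In the last two rows the numerator is the latest drug-stop week that still leaves a short window, for example 12 − 4.3 = 7.7.

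**Step 3: how many of these would be untransfused.** Assume Poisson transfusion episodes at an unchanged rate λ per 4 weeks, so P(none in t weeks) = exp(−λt/4). The rate is an assumption.

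| Episode rate | 2 weeks | 3 weeks | 4 weeks | 8 weeks | 12 weeks |
|---|---|---|---|---|---|
| 1 per 4 weeks | 61% | 47% | 37% | 14% | 5% |
| 1 per 8 weeks | 78% | 69% | 61% | 37% | 22% |
| 1 per 12 weeks | 85% | 78% | 72% | 51% | 37% |

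**Step 4: illustration with no true change.** Let e be the share of dependent subjects leaving early, t the weeks they are observed, and W the window. The apparent conversion is (1 − e)·exp(−λW/4) + e·exp(−λt/4). Take e = 5%, a value inside the range from Step 2, and one episode per 4 weeks.

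- 12-week version, t = 2: 0.95 × 0.050 + 0.05 × 0.607 = 7.8%. With t = 4 it is 6.6%. With full follow-up for everyone it is 5.0%.
- 8-week version, t = 2: 0.95 × 0.135 + 0.05 × 0.607 = 15.9%. With t = 4 it is 14.7%. With full follow-up it is 13.5%.

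If the early leavers stay in N but are not counted as converted, the results are 0.95 × 0.050 = 4.7% and 0.95 × 0.135 = 12.9%. At one episode per 8 weeks, the 12-week version gives 25.1% (t = 2) or 24.2% (t = 4), against 22.3% with full follow-up. If the follow-up phase counts, t is at least about 4.3 weeks except for subjects who die or miss that visit, so the t = 2 cases then apply to few.

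**The case against.** The strongest reply is that little rests on this table. Transfusion independence is not a co-primary, safety or secondary endpoint in either document. Its summary sits in SAP Section 6 with baseline, exposure and disposition, and Table 14.1.6.1 is listed among the baseline characteristics. It shows both directions of change, with no test or confidence interval. That stands. A reader might infer that the plan sets up a benefit claim on transfusion independence; the documents make none.

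Second, SAP 5.9.5 never says that a three-week subject is independent, and Protocol 8.4 counts screening and baseline as participation, so the window might reach back before Day 1. The shell's limit to time after Day 1 contradicts that. The roughly 4 weeks of screening and baseline would in any case not guarantee 8 or 12.

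Third, follow-up also counts as participation in Protocol 8.4, which reduces the affected share as in Step 2. That stands, with a reservation: SAP Table 2 schedules a transfusion review at the follow-up visit, but Protocol Table 3 and Section 9.5 do not. Those weeks could pass as transfusion-free for want of data.

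Fourth, other outputs reveal short follow-up: monthly units in Table 14.1.6.2, duration bands in Table 14.3.1.1, disposition in Table 14.1.1 and the transfusion listing. They help a careful reader but do not correct the shift counts.

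A reader might also infer that the rule can only inflate conversion. That holds against full follow-up at an unchanged rate. Against simply excluding short follow-up, the rate can move either way, because early leavers who were transfused stay in the denominator as not converted.

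**Conclusion.** The point holds as a minor defect in a stated rule. Applied literally, SAP 5.9.5 and the Table 14.1.6.1 shell can count an early leaver, or a subject cut off early, as converted to independence, and can miss conversions to dependence. Relative to full follow-up, both make a descriptive summary look more favourable. No alpha, power or endpoint depends on it.

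The share of subjects exposed is about 8% or 5% (12- and 8-week versions) if participation ends at drug stop, and about 4.5-5.1% or 1.8-2.5% if the follow-up phase counts. These shares rest on even dropout, on the same rate in dependent subjects, and on an interim 16% that was still immature. It would be tempting to read 8 and 5 as the percentage points of inflation, or as upper limits. They are neither: timing within the 24 weeks is not reported, dependent subjects may leave at a different rate, and only untransfused leavers are misclassified. Under Step 4's assumed rates, 5% early leaving adds about 1 to 3 points.

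**What to change.** In SAP 5.9.5, require at least 8 (12) weeks of post-Day 1 observation with transfusion data before the independent label is assigned. State whether the follow-up phase counts as observation.

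In Table 14.1.6.1, add a row for follow-up under 8 (12) weeks, not evaluable, in both baseline-status groups. Keep these subjects in N, count them in neither shift, and show their number. Splitting that number into transfused and not transfused would keep visible any baseline-independent subject who was transfused before leaving. Apply the same rule to the post-baseline proportion in SAP 6.8.

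The row must cover both groups. The shell is binary, so withholding the independent label without a third category could push an untransfused baseline-independent early leaver into the independent-to-dependent count.

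The cost is a sentence or two in the SAP, one extra table row and a slightly lower stated conversion rate. If follow-up weeks are to count, the difference between SAP Table 2 and Protocol Table 3 on transfusion review at that visit must also be reconciled.
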